4. SELECTION AND ENROLLMENT OF PARTICIPANTS

Patients will be recruited from up to 20 primary care clinics within Advocate Aurora Health that have agreed to implement the Pathway Platform. We aim to identify clinics that are representative of different geographic locations, patient populations, and care models for depression management, including behavioral health integration models. We will balance clinic diversity with feasibility to conduct this study. For example, we will only include clinics that have integrated Epic within their workflow so that the care team can easily access data collected from the patient in the Pathway Platform. We will also focus on clinics that have a large volume of patients diagnosed with depression as well as clinics that have care team members that are interested and engaged in depression care.

All care team members who care for patients with depression will be invited to participate in this implementation study and will have access to an online educational resource center. Patients fulfilling the following criteria will be eligible to download and use the Pathway Platform:

4.1 Inclusion

1. Adult aged 18 and above

2. Diagnosis with major depressive disorder or reference to “clinical depression” in patient charts. See **Appendix 1** for ICD codes for major depressive disorders
3. Recently prescribed monotherapy antidepressant medication (defined as new start, medication switch, or dose change in the past 3 months (**Appendix 2**).
4. Patients with inadequate response or tolerability concerns determined based on A PHQ-2 score of 3 or greater, or a PHQ-2 <3 with a PHQ-9 score of 5 or greater recorded in medical records in the past 6 weeks or during screening,
5. Able and willing to provide informed consent
6. Able to use the Pathway Platform based on clinician’s judgment, e.g. owns an iPhone version 5 or later or smartphones with Android operating systems, have an active data plan or regular WiFi access.

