3.1 Performance among participating clinics post-implementation

The Pathway Platform will be implemented in up to 20 primary care sites within the Advocate Aurora Health system and enroll a total of 200 patients for six-month duration. The visit where the patient has been onboarded to the Pathway Platform will be the enrollment visit (Figure 1). During the post- implementation period, data on patient outcomes will be collected through the Pathway Platform. At the end of the study an electronic and manual chart review for patients using the Pathway Platform will be conducted among participating clinics and performance related to measurement-based care, shared decision making and collaborative care, where applicable, will be assessed over the post-implementation period.

3.2 Retrospective Assessment: pre-implementation performance at the clinic level (before Pathway Platform implementation)

To assess Advocate's primary care sites performance pre-implementation, an electronic and manual chart review will be conducted from the same Advocate primary care clinics participating in the implementation study. Patients with a clinic visit at least 6 months prior to implementation (index visit) of the Pathway Platform and meeting the inclusion criteria for enrollment in the study, will be included in this analysis (figure 1). Patient history will be evaluated for three months prior to index visit to confirm eligibility. The goal is to capture patients with a new start, dose adjustment or switch of an antidepressant medication 6 months prior to the implementation index date (three-month inclusion window for patient identification). Six months of patient history will be “retrospectively” collected for this baseline patient cohort to assess the primary outcome, defined as PHQ-9 utilization, and other secondary outcomes outlined in the protocol. This analysis will serve as the comparison control for the primary and secondary outcomes to compare performance at the same clinics pre and post-implementation of the Pathway Platform. Depending on the number of eligible patients identified per site (20 per site), group level matching for age and sex may be conducted. The primary endpoint will be the proportion of patients with at least 2 PHQ-9 scores.

Figure 1: Study schematic

* Primary and secondary outcomes will be evaluated at 6 months, data collected beyond 6 months will be used for exploratory analysis

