4.2 Exclusion

1. Missing PHQ-2/PHQ-9 score in the past 6 weeks and/or unable to perform PHQ-2/PHQ-9 at index visit
2. Diagnosis with bipolar depression, schizophrenia, and/or schizoaffective disorder, (**Appendix 1**).
3. Patient no longer under primary care for depression and has transitioned to a psychiatric care team (i.e., Psychiatrist, Advance Practice Psychiatric Nurse, Psychiatric Nurse Practitioner, Psychiatric Physician Assistant).
4. Lack of functional English literacy (indicated by primary language in EMR).

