8.3.2 Secondary outcome

Process outcomes: The following secondary process outcomes will be compared between patients attending clinics pre- and post- implementation of the Pathway Platform.

- Measurement- based care: The proportion of patients reflecting measurement-based care informed MDD treatment adjustments in their charts, defined as at least one dose change, medication switch, or add on medication during the study period. The frequency and types of treatment adjustments will also be explored.
- Shared- decision making: The proportion of patients reflecting shared-decision making, using the OPTION12 Tool framework.²⁶ The tool will be modified by adding a thirteenth domain inquiring about goal setting (Asking the patient or caregiver about goals of treatment). The frequency and domains of shared-decision making will also be explored in a manual chart review and a variable added to assess if the clinician documented asking the patient about their goals of treatment.
- Referrals to behavioral health: The proportion of patients with at least one referral will be compared. The frequency and types of referrals will also be explored.
- Follow-up after hospitalization for mental illness: The proportion of hospitalized adults who receive follow-up within 7 days of discharge and within 30 days of discharge.
- Follow-up after emergency department visit for mental illness: The proportion of adults

who receive follow-up within 7 days of discharge and within 30 days of ED visit.

- Healthcare resource utilization: Number and costs associated with hospital admission, length of stay, emergency room admissions, and encounters with outpatient clinics. Costs will be calculated using USA national average costs for inpatient and outpatient visits or using an average Advocate Health Care system cost.

Patient clinical outcomes: The following outcomes will be compared between patients attending clinics pre- and post- implementation of the Pathway Platform, keeping in mind that the number of patients with these measures in the pre- implementation patient group will be limited:

- MDD remission: The proportion of patients with PHQ-9 ≤ 5 at the end of the study period. The last measurement available during the study period will be used to calculate remission.
- MDD response: The proportion of patients with a 50% or greater reduction in PHQ-9 scores. The first and last scores available during the study period will be used to calculate response.

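### Inclusion criterion 4 labels a symptom cutoff as inadequate response or tolerability concerns, and the unadjusted pre/post comparisons ignore the type and timing of the antidepressant change, so a different mix between cohorts could shift response and remission

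*Combined protocol and SAP*

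**What the plan says.** Section 4.1 has two linked criteria. Criterion 3 requires a recently prescribed monotherapy antidepressant, "defined as new start, medication switch, or dose change in the past 3 months". Criterion 4 admits "Patients with inadequate response or tolerability concerns determined based on A PHQ-2 score of 3 or greater", or a PHQ-2 below 3 with a PHQ-9 of at least 5, "recorded in medical records in the past 6 weeks or during screening". Section 4.2 excludes patients with "Missing PHQ-2/PHQ-9 score in the past 6 weeks and/or unable to perform PHQ-2/PHQ-9 at index visit". Nothing states whether the score must come before or after the medication change.

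Section 3.2 builds the pre-implementation cohort from charts. Patients with a visit at least 6 months before implementation and "meeting the inclusion criteria for enrollment in the study, will be included in this analysis". The section adds a three-month look-back to confirm eligibility and states the aim of finding patients with a "new start, dose adjustment or switch of an antidepressant medication 6 months prior to the implementation index date", with a three-month identification window. Matching on age and sex is optional.

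Section 8.3.2 defines response as a PHQ-9 reduction of 50% or more: "The first and last scores available during the study period will be used to calculate response". Remission uses the last score. Section 8.4 compares categorical outcomes by Pearson chi-square. The subgroup list in section 8.3.3 names baseline PHQ-9 severity and other characteristics, but not the type of medication change.

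**The concern.** The label and the rule do not match. A patient scored at the visit where a first antidepressant is prescribed meets a criterion called inadequate response before there is any treatment to respond to. A patient with side effects, a PHQ-2 below 3 and a PHQ-9 below 5 fails the criterion that names tolerability. A report that repeated the label would misdescribe who was studied.

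The analytic issue follows from the pooling. If patients who have just started treatment tend to change differently on the PHQ-9 from patients whose treatment was switched or adjusted, the response and remission rates of a cohort depend on its mix. In a non-randomised pre/post comparison nothing guarantees that the mix is the same, and the plan neither reports it nor adjusts for it.

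**Working it through.** **The plan's own figure.** Section 8.2 gives 100 per group for 75% versus 90%, two-sided alpha 0.05, 80% power. With the pooled two-proportion formula, n = [1.96·√(2·0.825·0.175) + 0.8416·√(0.75·0.25 + 0.90·0.10)]² / 0.15² = (1.0532 + 0.4433)² / 0.0225 = 99.5, so 100. It reproduces, and this point does not alter it.

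**Order of score and change.** The change may be up to 3 months old and the score up to 6 weeks old. If the change is more than 6 weeks old, a score within the window must follow it. If the change is more recent, the score may come before it, on the same day, or after it. The problem is therefore confined to changes in the last 6 weeks.

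**Tolerability.** PHQ-2 and PHQ-9 are the only instruments in criterion 4. Side effects are collected by the app's daily check-in (section 4.4.1), after enrolment and in the post cohort only.

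**Assembly of the cohorts.**
- Post: flagged from clinic schedules, introduced by the care team, consented, and able to qualify on a score taken at screening (sections 4.1 and 4.3).
- Pre: found in charts, so dependent on a score that routine care recorded. The timing text in section 3.2 can be read in two ways. Either the medication change sits at the 6-month mark where follow-up begins, or it lies anywhere in the three months before the index visit, as in the post cohort.

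**Illustration with no Platform effect.** Cohort response = s·r_new + (1 − s)·r_other, where s is the share of new starts. The documents give neither s nor the rates, so all are assumed. The rejection probability is the exact binomial probability that the two-sided Pearson chi-square exceeds 3.84.

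| r_new / r_other | s pre / post | Response pre / post | Rejection, 200 vs 200 | Rejection, 100 pre vs 200 post |
|---|---|---|---|---|
| 45% / 25% | 30% / 30% | 31% / 31% | 5.0% | 5.0% |
| 40% / 30% | 30% / 50% | 33% / 35% | 7.1% | 6.3% |
| 40% / 30% | 30% / 60% | 33% / 36% | 9.8% | 8.0% |
| 45% / 25% | 30% / 50% | 31% / 35% | 13.6% | 10.4% |
| 45% / 25% | 30% / 60% | 31% / 37% | 24.6% | 17.5% |
| 50% / 25% | 30% / 60% | 32.5% / 40% | 34.7% | 24.3% |

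Example: 0.30·45% + 0.70·25% = 31%, and 0.60·45% + 0.40·25% = 37%. Exchanging the shares between cohorts reverses the sign, and the rejection rate at 200 per group is unchanged. The last column assumes that only 100 pre patients have scores. Section 8.3.2 warns that the number will be limited but gives no figure.

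**The case against.** The strongest reply is that section 3.2 puts the pre cohort under the same inclusion criteria and gives it a three-month look-back. A loose label applied equally to both cohorts creates no bias, and the first row of the table shows this. That stands.

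A reader might go further and infer that the cohorts do differ in their share of new starts, or that the pre clock starts at the medication change while the post clock starts later. The documents do not support either. They give no share for any cohort, the look-back lets a pre patient be indexed up to three months after the change, and nothing prevents a post patient from enrolling on the day a drug is started. The different starting clock is one reading of ambiguous wording.

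It is also fair to say that the larger rejection rates need both a 20 to 25 point response gap and a 20 to 30 point imbalance, that they fall when fewer pre patients are scored, and that the different course of new starters is an assumption not stated in the plan. The subgroup list is open-ended and does not rule out event type. The label appears only in criterion 4, not in the objectives, so misreporting is a risk rather than a fact.

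What remains is the mismatch of label and rule, and a plausible confounder in differently assembled cohorts for which no adjustment is planned. An open subgroup list does not adjust the main comparison. Baseline severity alone does not separate a new starter from a dose-changed patient with the same score.

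**Conclusion.** The point holds in a limited form. Criterion 4 measures current depressive symptoms, not response to treatment or tolerability, and for changes in the last 6 weeks the score need not follow the change. This does not itself bias the comparison. A difference between cohorts in event type or time since the event could shift response and remission with no Platform effect, and the planned tests would not reveal it. Under the assumed inputs, false rejection runs from about 7% to 35% at 200 per group, or about 6% to 24% with 100 pre patients scored, against a nominal 5%. Neither the existence nor the direction of an imbalance is shown.

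A reader might infer that the primary result is compromised. The documents do not support that: PHQ-9 utilization could depend on how recent the treatment change is, but nothing here quantifies it. The point warrants a change to the analysis plan and does not call the design into question.

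**What to change.** 1. Keep the cutoffs. Describe criterion 4 as current depressive symptoms, and do not report the sample as inadequate responders or as having tolerability concerns.
2. From the eligibility review, derive three variables for every patient in both cohorts: event type (new start, switch, dose change), days from the event to the index or enrolment visit, and whether the qualifying score came before, on, or after the event date.
3. Tabulate these by cohort.
4. Add event type and time since the event, alongside baseline PHQ-9, as stratification or adjustment variables in the pre/post comparisons of response and remission. Apply the same adjustment as a sensitivity analysis for PHQ-9 utilization. Because a patient can qualify on PHQ-2 alone, state which PHQ-9 serves as baseline.
5. Reconcile the timing wording in section 3.2 with the three-month window in criterion 3. Whether the score must follow the medication change is for the sponsor to settle.

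The cost is some rewording, three variables from records already reviewed for eligibility, and a stratified or regression analysis. Intervals will be slightly wider if the mix differs between cohorts.

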4.2 Exclusion

1. Missing PHQ-2/PHQ-9 score in the past 6 weeks and/or unable to perform PHQ-2/PHQ-9 at index visit
2. Diagnosis with bipolar depression, schizophrenia, and/or schizoaffective disorder, (**Appendix 1**).
3. Patient no longer under primary care for depression and has transitioned to a psychiatric care team (i.e., Psychiatrist, Advance Practice Psychiatric Nurse, Psychiatric Nurse Practitioner, Psychiatric Physician Assistant).
4. Lack of functional English literacy (indicated by primary language in EMR).

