The Pathway Platform consists of a mobile app for patients and a care team interface that can be accessed through Epic. We intend to enroll 200 patients who meet the eligibility criteria for this study and agree to download the Pathway Platform. An additional 200 patients will be identified from the same participating clinics to form the pre-implementation cohort. These are patients who visited the participating clinics at least 6 months prior to study implementation; they will not be actively enrolled into the study and their data will be collected retrospectively through chart reviews and electronic data pulls.

LIST OF ABBREVIATIONS

AE	Adverse Event
APA	American Psychiatric Association
APPS	Mobile Health Applications
ASEX	Arizona Sexual Experience Scale
CCM	Collaborative Care Model
DSST	Digit Symbol Substitution Test
ED	Emergency Department
EMR	Electronic Medical Record
GAD	Generalized Anxiety Disorder
GAS	Goal Attainment Scale
GAD	Generalized Anxiety Disorder
IRB	Institutional Review Board
IQR	Interquartile Range
MBC	Measurement Based Care
MDD	Major Depressive Disorder
PAM-13	Patient Activation Measure
PDQ-D5	Perceived Deficits Questionnaire- Depression
PHQ-2	Patient Health Questionnaire-2
PHQ-9	Patient Health Questionnaire Depression
PROMIS	Patient-Reported Outcomes Measurement Information System
PSD-6	PROMIS Sleep Disturbance 6a
PTSD	Post-Traumatic Stress Disorder
SAE	Serious Adverse Event
SD	Standard Deviation
SDM	Shared-Decision Making Model
SSR	Special Situation Report
WSAS	Work and Social Adjustment Scale
WHO-5	World Heart Organization- Five Well Being Index

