4.3 Study Enrollment Procedures

This is a real-world implementation study with minimal interaction between the study team and patients. To address recent virtual visits in primary care due to COVID-19 and for the safety of the study team, study methods were developed to adapt virtual patient recruitment and e-consent during existing virtual visit processes. An in person consenting process is also available for in person clinic visits, when safe and appropriate, and will be supported by a study team member present at recruiting clinics.

Study team will review clinic schedules routinely for visits scheduled the next day and will flag potentially eligible patients and will discuss the list with the health care team. These patients will be introduced to the study opportunity by care team members during routine clinic visits.

- Consenting in person: If the patient is interested, they will be roomed with a study team member who will confirm study eligibility and provide written informed consent. If the patient is eligible and provides consent, the study team will share a secure message with a link for the Pathway App with the patient and the patient will be able to activate the Pathway App and start entering data. The secure message will be shared with the patient via AAH's secure patient portal. Or through an email for patients who have not activated their portal. The invitation message in the email will include an individualized link to download the App with a unique code specific to that patient to ensure security.

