8.3 Outcomes

8.3.1 Primary outcome

The primary process outcome is PHQ-9 utilization over a six-month period. For purposes of this study, PHQ-9 utilization will be defined as documentation of at least 2 PHQ-9 scores in the EMR over the initial 6-month study period. The proportion of patients who meet this definition will be compared between patients attending clinics pre- and post- implementation of the Pathway Platform. Additional analyses exploring the number of PHQ-9s over the study period will also be conducted.

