8.4 Data analysis

For primary and secondary hypothesis testing, process measures, patient clinical outcomes, and health care resource utilization will be compared pre- and post- implementation of the Pathway Platform.

Additional patient reported outcomes will be compared among patients using the Pathway Platform only at baseline and end of study. For pre-implementation, outcomes will be assessed among patients who visited one of the study clinics at least once over the pre-implementation study period and were eligible to use the Pathway Platform, if it had been available. For the post-implementation period, the Pathway Platform will be the data source for paired t-test analysis, assessing change in continuous variables including PHQ-9 scores. Categorical outcomes will be presented as proportions and compared using Pearson Chi2 test. Continuous outcomes will be assessed for normality and presented as means and standard deviations (SD) or medians and interquartile ranges (IQR); continuous outcomes will be compared using Student's t test for independent groups. Two-tailed tests using a significance threshold of $p < 0.05$ will be used for all tests.

Exploratory outcomes: will be described among patients attending the pathway platform clinics only and will be compared between baseline, 6-month and extended follow up. Change in these outcomes overtime, including utilization analytics will also be explored. Categorical outcomes will be presented as proportions and compared using McNemars' test. Continuous outcomes will be assessed for normality and presented as means and standard deviations (SD) or medians and interquartile ranges (IQR); continuous outcomes will be compared using Student's Paired t test for single group comparison. Two-tailed tests using a significance threshold of $p < 0.05$ will be used for all tests. Goal attainment will be summarized by proportion of patients who achieve their identified goals based on the set time bound duration of the goal (i.e., GAS Score ≥ 50).^{29,30} The goal attainment scale adapted for depression yields a norm-based score (standardized to a mean of 50, SD of 10) at baseline and at the end of the time bound goal; the change from score from baseline will also be summarized.

System level performance: Process outcomes will be evaluated at the system level (all primary

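### A pre-implementation patient qualifies only with a PHQ score that routine care recorded, while a post-implementation patient can also be scored at screening, so the two cohorts are not selected alike

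*Combined protocol and SAP*

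**What the plan says.** Section 4.1, inclusion 4, requires a PHQ-2 of 3 or more, or a lower PHQ-2 with a PHQ-9 of 5 or more, "recorded in medical records in the past 6 weeks or during screening". Section 4.2, exclusion 1, removes patients with "Missing PHQ-2/PHQ-9 score in the past 6 weeks and/or unable to perform PHQ-2/PHQ-9 at index visit".

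Section 3.2 builds the pre-implementation cohort from patients with an earlier clinic visit and "meeting the inclusion criteria for enrollment in the study, will be included in this analysis". Section 8.4 describes the same cohort as patients who "were eligible to use the Pathway Platform, if it had been available". The Sample Size and Population summary says of them that "they will not be actively enrolled into the study and their data will be collected retrospectively through chart reviews and electronic data pulls".

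Post-implementation patients are screened prospectively. Section 4.3 says that, when consent is taken in person, "they will be roomed with a study team member who will confirm study eligibility and provide written informed consent"; when consent is electronic, the research team confirms eligibility before sending the invitation.

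For the primary outcome, section 8.3.1 states that "PHQ-9 utilization will be defined as documentation of at least 2 PHQ-9 scores in the EMR over the initial 6-month study period". Section 8.4 compares the cohorts with an unadjusted Pearson chi-square test. The only balancing mentioned is possible group-level matching on age and sex (section 3.2).

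**The concern.** The same eligibility text works differently in the two cohorts. A post-implementation patient with no recent score can be scored during screening and enrolled. A pre-implementation patient with no recorded score cannot be scored after the event and drops out. The control group then holds only patients whose clinic had recently used a PHQ, and the endpoint is whether clinics use the PHQ-9.

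Two things are at stake. The cohorts are not like-for-like on a characteristic close to the outcome, and neither the unadjusted test nor matching on age and sex addresses that. The reported pre-implementation rate would also describe patients already being measured, and not usual practice at these clinics.

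**Working it through.** **1. The routes to eligibility, side by side**

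| | Pre cohort | Post cohort |
|---|---|---|
| Score in the chart within 6 weeks | Qualifies | Qualifies |
| PHQ done by the clinic at the index visit | In the chart, so qualifies | Qualifies |
| No score until screening supplies one | Not possible (charts only) | Qualifies under inclusion 4 |

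The third row is the asymmetry. It follows from inclusion 4 together with the chart-only construction of the pre cohort. Exclusion 1 does not show it alone.

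**2. The two readings of exclusion 1**

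- Read as 'and', it removes only patients with no recent score who also cannot be scored at the index visit. This agrees with inclusion 4 and leaves the asymmetry in place.
- Read as 'or', a missing score in the past 6 weeks is enough to exclude in either cohort. The asymmetry goes, but patients admitted by inclusion 4 through screening are now excluded.

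The two criteria need reconciling on either reading.

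**3. The plan's own figure**

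Inputs from section 8.2: 75% pre, 90% post, two-sided alpha 0.05, power 80%, Pearson chi-square. With the pooled rate 0.825:

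n = [1.960·√(2·0.825·0.175) + 0.842·√(0.75·0.25 + 0.90·0.10)]² / 0.15² = 99.5, so 100 per group.

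This reproduces the plan. Power is 80.2% at 100 per group and 97.9% at the chosen 200 per group.

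**4. Selection taken alone (assumed inputs)**

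The documents give no utilization rate for patients without a recorded score. Let r be the share of otherwise eligible pre patients who have one, let their utilization be the plan's 75%, and let u be utilization in the rest.

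Rise in the pre rate = (1 − r)·(0.75 − u)

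| r | u = 25% | u = 50% | u = 75% |
|---|---|---|---|
| 50% | 25 points | 12.5 | 0 |
| 70% | 15 | 7.5 | 0 |
| 90% | 5 | 2.5 | 0 |

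**5. The opposite push (assumed inputs)**

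No section says whether a qualifying or screening PHQ-9 counts toward the two. App PHQ-9s, prompted every two weeks, are also stored in the EMR (sections 4.4.1 and 4.4.2). Suppose study- or app-delivered scores alone turn a fraction c of the 25% who would otherwise miss the endpoint into successes:

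Post rate = 0.75 + 0.25·c

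For c = 25, 50 and 75% this gives 81.3, 87.5 and 93.8%, a rise of 6.3, 12.5 or 18.8 points with no change in clinician practice. This range overlaps the one in step 4, so the sign of the net effect is open.

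**6. Power of a subset with routine-care scores only**

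Take 200 pre patients, n post patients, and 75% against 90%. For n = 100, the pooled rate is (200·0.75 + 100·0.90)/300 = 0.80. The null standard error is √(0.80·0.20·(1/200 + 1/100)) = 0.0490, and the alternative standard error is √(0.1875/200 + 0.09/100) = 0.0429. Then (0.15 − 1.960·0.0490)/0.0429 = 1.26, so power is 89.6%. With 130 and 160 post patients it is 94.1% and 96.4%. The subset sizes are assumptions.

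**The case against.** A reader might infer that the trial's effect is biased downward and that power falls. The documents do not support that. If a screening PHQ-9 is recorded in the EMR and counts, the same route gives post patients one of their two scores and pushes the difference up. A power loss can be produced only by also lowering the post rate below the planned 90%, on a share of screened patients and a utilization gap that appear nowhere in the documents. If 75% and 90% are the rates in the cohorts as selected, the difference is still 15 points and power is still 97.9%; the selection then changes what the baseline means.

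Other limits also stand:

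- A PHQ-2 of 3 or more qualifies alone, while the endpoint counts PHQ-9 scores. The selection is on related behaviour and not always on the endpoint itself.
- A PHQ done by the clinic at a pre patient's index visit would be in the chart, so not every pre patient first measured at that visit is lost.
- No section says that study staff administer the PHQ. Section 4.3 describes minimal study-team contact, and Table 1, as far as its layout can be read, gives the EMR and patient scheduling as the source at screening. The number of post patients qualifying only through screening may be small.
- Section 3.2 applies only the inclusion criteria by name to the pre cohort. Inclusion 4 is enough to create the asymmetry.

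None of this removes the unequal route. Opposing influences of unknown size cannot be assumed to cancel.

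**Conclusion.** The concern holds in a limited form. On the wording of inclusion 4, a patient without a recorded score can enter the post cohort but not the pre cohort. This selects the comparison group on behaviour related to the primary endpoint, and no planned analysis deals with it. Exclusion 1 conflicts with inclusion 4 if its connective is read as 'or'.

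The selection component, taken alone, raises the pre rate and attenuates the difference. Its illustrated range of 0 to 25 points rests wholly on assumed values of r and u. The net direction and size are not determined by the documents, and no loss of power should be quoted. The sample-size calculation is unaffected: 100 per group reproduces.

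**What to change.** 1. Reconcile exclusion 1 with inclusion 4, and state one rule for the qualifying score that applies to both cohorts, including how it is applied to charts.
2. Record for every patient whether the qualifying score was chart-recorded in routine care or obtained at study screening.
3. State whether the qualifying or screening score counts toward the two PHQ-9 scores. Pre-specify a supporting analysis that leaves it out of the count in both cohorts.
4. Pre-specify a second supporting analysis limited to patients with a routine-care qualifying score in both cohorts.
5. Report pre-implementation utilization without the score criterion as descriptive context only. Inadequate response cannot be confirmed in those patients, so this does not measure the size of the selection.

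The cost is one data flag, two supporting analyses, one relaxed data query and a wording change. The routine-score subset is smaller, but with 100 to 160 post patients against 200 pre, power for 75% against 90% is still about 90 to 96%. The subset has its own weakness. Care teams are trained in measurement-based care before they enrol patients, and clinics receive audit and feedback (section 4.4.3), so a routine score in the post period may itself reflect the intervention. These analyses therefore support the primary comparison and do not replace it.
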